## **9.6                    PROTOCOL AMENDMENTS**

Any protocol amendments will be prepared by the Sponsor. Protocol amendments will be submitted to the IRB/EC and to regulatory authorities in accordance with local regulatory requirements.

Approval must be obtained from the IRB/EC and regulatory authorities (as locally required) before implementation of any changes, except for changes necessary to eliminate an immediate hazard to patients or changes that involve logistical or administrative aspects only (e.g., change in Medical Monitor or contact information).

**Appendix 1**  
**Schedule of Activities for Patients with Follicular Lymphoma:**  
**Dose-Escalation and Expansion Phases**

Assessment/Procedure	Screening a		Induction (Six 28-Day Cycles)								EOI	Maintenance (24 Months) d	EOM b	Post-Tx Follow- Up Period (Q3M) e	Survival Follow- Up Period (Q3M) e
	Days -28 to -1	Days -14 to -1	Cycle 1 (±1 day)				Cycle 2 (±2 days)		Cycles 3-6 (±2 days)		After Last Induction Dose c		35 Days after Last Dose		
			D 1	D 5	D 8	D 15	D 1	D 15	D 1	D 15					
Informed consent(s) f	x														
Demographic data	x														
Medical history	x														
ECOG performance status	x														
Vital signs g	x		x		x	x	x		x		x h	x i	x		
Height	x														
Weight and BSA	x														
Triplicate 12-Lead ECG	x		x j	x j					x j		x	x j	x		
MUGA or ECHO	x k								x k		x k		x k		
Complete physical examination l, m	x														
Targeted physical examination m, n							Day 1, Cycles 2 and 4				x	x i	x	x	
Ann Arbor, FLIPI, and FLIPI2	x														
B symptoms o	x														

**Appendix 1**  
**Schedule of Activities for Patients with Follicular Lymphoma:**  
**Dose-Escalation and Expansion Phases (cont.)**

Assessment/Procedure	Screening a		Induction (Six 28-Day Cycles)								EOI	Maintenance (24 Months) d	EOM b	Post-Tx Follow- Up Period (Q3M) e	Survival Follow- Up Period (Q3M) e
	Days -28 to -1	Days -14 to -1	Cycle 1 (± 1 day)				Cycle 2 (± 2 days)		Cycles 3-6 (± 2 days)		After Last Induction Dose c		35 Days after Last Dose		
			D 1	D 5	D 8	D 15	D 1	D 15	D 1	D 15					
β 2 microglobulin			x												
Hematology p		x	x q,r		x r	x r	x r	x	x r	x	x h	x i	x		
Serum chemistry s		x	x q,r		x r	x r	x r	x	x r	x	x h	x i	x		
Coagulation (INR, aPTT [or PTT], and PT)		x													
Pregnancy test t		x									x h		x		
Hepatitis B and C, testing u	x														
Quantitative IgA, IgG, and IgM			x								x	x v	x	x w	
PK sample for obinutuzumab			x x												
PK sample for idasanutlin			x x												
PK sample for venetoclax			x x												
Exploratory biomarker samples			x x												

**Appendix 1**  
**Schedule of Activities for Patients with Follicular Lymphoma:**  
**Dose-Escalation and Expansion Phases (cont.)**

Assessment/Procedure	Screening a		Induction (6 Cycles; 28-Day Cycles)								EOI	Maintenance (24 Months) d	EOM b	Post-Tx Follow-Up Period (Q3M) e	Survival Follow- Up Period (Q3M) e	
	Days -28 to -1	Days -14 to -1	Cycle 1 (± 1 day)				Cycle 2 (± 2 days)		Cycles 3-6 (± 2 days)		After Last Induction Dose c		35 Days after Last Dose			
			D 1	D 5	D 8	D 15	D 1	D 15	D 1	D 15						
Blood for MRD y			x r					x				x	x v	x		
Blood for lymphocyte immunophenotyping z			x r			x r	x r			x r		x	x v	x	x w	
Optional serum for RBR aa			x	x												
Tumor tissue specimen (remaining tissue may be used for optional RBR specimen bb )	x bb		x cc													
Concomitant medications		x	To be recorded continually until end of treatment													
Adverse events dd		x	To be assessed continually dd													
PET-CT scan	x ee											x ff	x gg			
CT scan hh	x hh							x ii				x ff	x jj	x kk	x ll	
Bone marrow biopsy and aspirate	x mm											x ff, nn	x nn	x kk, nn		
New anti-lymphoma treatment															x	x
Survival follow-up																x

## Appendix 1

### Schedule of Activities for Patients with Follicular Lymphoma: Dose-Escalation and Expansion Phases (cont.)

---

BSA=body surface area; CT=computed tomography; D=day; DLBCL=diffuse large B-cell lymphoma; ECG=electrocardiogram; ECHO=echocardiogram; ECOG=Eastern Cooperative Oncology Group; eCRF=electronic Case Report Form; EOI=end of induction; EOM=end of maintenance; FL=follicular lymphoma; FLIPI (2)=Follicular Lymphoma International Prognostic Index (2); MRD=minimal residual disease; MRI=magnetic resonance imaging; MUGA=multigated acquisition; PET=positron emission tomography; PK=pharmacokinetic; Q3M=every 3 months; RBR=Roche Biosample Repository; TLS=tumor lysis syndrome; Tx=treatment.

Notes: On treatment days, all assessments should be performed prior to dosing, unless otherwise specified. Assessments shaded in gray should be performed as scheduled, but the associated data do not need to be recorded on the eCRF (except in the case of an adverse event).

- a The screening period starts with the signing of the Informed Consent Form, including the optional Informed Consent Form if appropriate. Results of standard-of-care tests or examinations performed prior to obtaining informed consent and within the defined window may be used as screening and baseline assessments; such tests do not need to be repeated for screening purposes.
- b Patients who complete maintenance treatment or discontinue maintenance treatment prematurely will undergo assessments at the EOM.
- c EOI assessments should be performed 6–8 weeks after Day 1 of the last induction cycle. As an exception, patients who discontinue induction treatment prematurely because of an adverse event may undergo EOI assessments 4–8 weeks after their last dose of study treatment.
- d Maintenance treatment should start 8 weeks ( $\pm$  1 week) after Day 1 of the final cycle of induction and will continue until disease progression or unacceptable toxicity for up to 2 years.
- e Patients who complete treatment or discontinue treatment for reasons other than disease progression will undergo assessments every 3 months during the post-treatment FU period, which will continue until disease progression, the start of new anti-lymphoma treatment, or the end of the study, whichever occurs first. The first post-treatment FU visit is 3 months after the EOI visit for patients who do not receive maintenance treatment and 3 months after the last dose for patients who receive maintenance treatment. Patients who experience disease progression or start another anti-lymphoma treatment will be evaluated for survival status and new anti-lymphoma treatment every 3 months during the survival follow-up period, which will continue until the end of the study. The end of the study is defined as the time when all enrolled FL patients have completed or discontinued study treatment and all enrolled DLBCL patients have been followed for at least 1 year after they have completed or discontinued study treatment.
- f Informed consent must be documented before any study-specific screening procedure is performed.
- g Vital signs include respiratory rate, pulse rate, body temperature, and systolic and diastolic blood pressures while the patient is in a seated position. For obinutuzumab infusions: For the first cycle and for patients who experience an infusion-related reaction, vital signs will be measured prior to the infusion, every 15 ( $\pm$ 5) minutes for the first 90 minutes of the infusion, and then every 30 ( $\pm$ 10) minutes until 1 hour after completion of the infusion. For the second and subsequent cycles, vital signs will be measured every 30 minutes during the infusion, except for patients who have experienced an infusion-related reaction during a prior infusion. For venetoclax, serial vital signs will be measured and TLS laboratory samples will be drawn (serum chemistry as defined in Section 4.5.6) prior to the first dose of venetoclax and 8, 12, and 24 hour post-dose.
- h Perform only for patients who will not be receiving maintenance treatment.

## Appendix 1

### Schedule of Activities for Patients with Follicular Lymphoma: Dose-Escalation and Expansion Phases (cont.)

---

- i Vital signs will be measured, a targeted physical examination will be performed, and hematology and serum chemistry will be assessed during maintenance every 2 weeks during the first month, every month until Month 6, and every 2 months thereafter.
- j All ECGs should be performed within 2 hours prior to idasanutlin administration and either 6 hours after idasanutlin administration or immediately after obinutuzumab administration, whichever occurs later. ECGs will be performed in triplicate on Days 1 and 5 of Cycles 1 and 4 in the induction phase. However, on Day 5 of Cycles 1 and 4 in the induction phase, the postdose ECG should be performed only if the patient is still at the clinic.
- k Perform MUGA or echocardiogram at screening (Day –28 to Day –1), on Day 1, Cycle 4, at the EOI, the EOM, and as clinically indicated.
- l Includes evaluation of the head, eyes, ears, nose, and throat and the cardiovascular, dermatological, musculoskeletal, respiratory, gastrointestinal, genitourinary, and neurological systems. Record abnormalities observed at baseline on the General Medical History and Baseline Conditions eCRF.
- m As part of tumor assessment, the physical examination should include evaluation for the presence of enlarged nodes, palpable hepatomegaly, and splenomegaly. This information will be recorded on the appropriate tumor assessment eCRF.
- n Includes systems of primary relevance (e.g., cardiovascular and respiratory systems), systems associated with symptoms (newly emergent or monitored from baseline), and areas associated with tumor assessment (lymph nodes, liver, spleen, and any other areas identified at baseline). Record new or worsened clinically significant abnormalities on the Adverse Event eCRF.
- o Unexplained fever > 38°C, night sweats, unexplained weight loss > 10% of body weight over 6 months.
- p Includes hemoglobin, hematocrit, platelet count, RBC count, WBC count, and percent or absolute WBC differential count (neutrophils, eosinophils, basophils, monocytes, lymphocytes, and other cells).
- q Screening laboratory assessments may be used for Day 1 of Cycle 1 if performed within 24 hours prior to Day 1 of Cycle 1. Additional hematology and serum chemistry samples must be drawn 0–4 hours pre-dose and 8 and 24 hours post-dose on Day 1 of Cycle 1 to monitor for TLS. Note that the 24-hour post-dose sample will be obtained on Day 2 of Cycle 1.
- r Perform hematology and serum chemistry tests within 72 hours prior to Day 1 of each cycle and within 24 hours prior to Days 8 and 15 of Cycle 1. Samples for exploratory biomarker research should be collected at the same time as hematology and serum chemistry samples.
- s Includes sodium, potassium, glucose, BUN or urea, creatinine, calculated creatinine clearance, calcium, total bilirubin, direct bilirubin, total protein, albumin, ALT, AST, alkaline phosphatase, amylase, lipase, LDH, and uric acid.
- t All women who are not post-menopausal ( $\geq 12$  months of non-therapy-induced amenorrhea) or surgically sterile will have a serum pregnancy test at screening within 7 days prior to Day 1 of Cycle 1. Because of the suspected effect of idasanutlin or venetoclax on embryo–fetal development, monthly pregnancy testing is strongly recommended for women of childbearing potential.
- u Includes hepatitis B surface antigen, total hepatitis B core antibody, and hepatitis C virus antibody.
- v Perform at the same time as tumor assessments at 12, 18, and 24 months after initiation of induction treatment.
- w Perform every 3 months until recovery to either normal range or baseline level, disease progression, or the start of new anti-lymphoma treatment, whichever occurs first.

## Appendix 1

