### **2.1 SAFETY OBJECTIVES**

- To determine the RP2Ds for idasanutlin and venetoclax when given in combination with a fixed dose of obinutuzumab or rituximab during the dose-escalation phase on the basis of the following endpoint:
  - Incidence of DLTs during the first two cycles of study treatment

- To evaluate the safety and tolerability of obinutuzumab or rituximab in combination with idasanutlin and venetoclax during the dose-escalation and expansion phases on the basis of the following endpoints:
  - Nature, frequency, severity, and timing of adverse events, including DLTs
  - Changes in vital signs, ECGs, and clinical laboratory results during and following study treatment administration

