### **Combination of Obinutuzumab, Idasanutlin, and Venetoclax in Patients with FL in the Bridging Cohorts**

Following the identification of the MTDs for idasanutlin and venetoclax in combination with obinutuzumab in Regimen A, *or following Sponsor decision based on clinical judgment*, a bridging cohort of patients with FL will be opened to *repeat the last dose tested* in a different regimen. Obinutuzumab will be given alone in Cycle 1 and in combination with idasanutlin and venetoclax from Cycle 2 to 6 (see [Figure 4](#) and [Table 1](#)). This regimen is referred to as Regimen B.

If safety and tolerability allow, idasanutlin and venetoclax dose escalation may be explored with Regimen B in patients with FL until identification of new MTDs (see [Figure 4](#)).

After the last patient in each cohort has completed the two-cycle DLT observation period, the Sponsor, in consultation with the investigators, will evaluate the next dose recommended according to the mCRM (see [Section 3.1.2.3](#)) and agree on doses for the subsequent cohort(s), taking into account relevant demographic, adverse event, laboratory, dose administration, and PK (if available) data. At each dose-escalation step, the dose may be escalated or de-escalated, or an additional cohort at the same dose level may be enrolled.

[figure not shown]
On the basis of review of real-time safety data from this study and all available data from Study BH29812, dose escalation may be halted or modified by the Sponsor as deemed appropriate.

Although the DLT assessment window is defined as the first two treatment cycles, cumulative toxicities occurring beyond the first two cycles may be considered when determining the MTDs for idasanutlin or venetoclax.

Multiple MTDs may be identified, and the most appropriate RP2Ds will be chosen on the basis of safety, PK, and PD data. At the end of dose–escalation phase, RP2Ds (one for idasanutlin and one for venetoclax) in combination with obinutuzumab and one regimen will be decided for patients with FL. RP2Ds (one for idasanutlin and one for venetoclax) in combination with rituximab will be decided for patients with DLBCL. The RP2Ds of idasanutlin and venetoclax, as well as the treatment regimens for patients with FL and DLBCL, may be different.

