the event a patient presents with an episode of Grade  $\geq 2$  supraventricular arrhythmia (e.g., atrial fibrillation, atrial flutter, sinus tachycardia), an unscheduled ECG should be reported. Standard-of-care treatment may be instituted at the discretion of the investigator. If a PK sample is not scheduled for that timepoint, an unscheduled idasanutlin PK sample should be obtained.

ECG sampling assessment windows are as follows:

- Pre-dose: within 2 hours prior to idasanutlin dosing
- Post-dose: 6 hours after idasanutlin dose ( $\pm 5\%$ ; equal to 18 minutes) or after the end of obinutuzumab or rituximab infusion, whichever occurs later

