**Appendix 1**  
**Schedule of Activities for Patients with Follicular Lymphoma:**  
**Dose-Escalation and Expansion Phases (cont.)**

**Study Treatment Administration: Dose Escalation for the Bridging Cohorts (Regimen B)**

Study Treatment	Induction (Six 28-Day Cycles)								Maintenance Every 2 Months a		
	Cycle 1 (±1 day)					Cycles 2–6 (±2 days)					
	Day 1	Day 5	Day 8	Day 10	Day 15	Day 1	Day 5	Day 10	Day 1	Day 5	Day 10
Obinutuzumab b (1000 mg IV)	x		x		x	x			x		
Idasanutlin b (PO QD)						Days 1–5			TBD c		
Venetoclax b (PO QD)						Days 1–5 or Days 1–10 d			TBD c		

IV = intravenous; PD = pharmacodynamic; PK = pharmacokinetic; PO = by mouth; QD = once a day; TBD = to be determined.

a Total duration of maintenance is 24 months for obinutuzumab and 6 months for idasanutlin and venetoclax.

b Refer to Section 4.3.2 for instructions on study treatment administration.

c Regimen will be defined based on available safety, tolerability, PK, and PD data.

d Regimen is defined according to the dose-escalation plan (see Section 3.1.2).

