### Appendix 3 Pharmacokinetic and Biomarker Sampling Schedule (cont.)

#### Dose-Escalation Phase (Induction Treatment for FL Patients; 28-Day Cycles) In Regimen B

Study Visit		Serum Obinutuzumab PK Sample a, b	Plasma Idasanutlin PK and Serum MIC-1 Sample c	Plasma Venetoclax PK Sample
Cycle 1	Day 1 d	Pre-infusion (any time prior to dose on that day); e 30 (± 10 min) after end of infusion	Pre-administration (any time prior to dose on that day) e	Pre-administration (any time prior to dose on that day)
	Day 5	—	—	—
Cycle 2	Day 1	Pre-infusion (within 5 hr prior to dose); 30 (± 10) min after end of infusion	Pre-administration (any time prior to dose on that day); 6 hr (± 20 min) post-idasanutlin administration	Pre-administration (any time prior to dose on that day); 6 hr (± 20 min) post-venetoclax administration

DLBCL = diffuse large B-cell lymphoma; FL = follicular lymphoma; PK = pharmacokinetic.

Note: A “—” indicates not applicable.

a Sample collection timing is relative to the specified drug.

b Samples collected for PK analysis may be used for additional PK, HAHA, and/or ATA assay development and validation, and additional immunogenicity characterization, at the discretion of the clinical pharmacologist and/or the clinical scientist.

c Two tubes for plasma and serum, respectively, at each sampling timepoint.

d If the Day 1, Cycle 1 dose of obinutuzumab is split over 2 days, take the 30 minutes post end of infusion obinutuzumab PK sample relative to the end of the infusion on Day 2, and ensure that the date and time of the PK collection are accurately recorded.

e The Day 1, Cycle 1 predose PK sample may be taken any time prior to the first dose that day.

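### Under Regimen B, the idasanutlin-timed ECGs fall in a cycle without idasanutlin or venetoclax, and the first scheduled ECG on these drugs is at Cycle 4

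*Protocol*

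**What the plan says.** Appendix 1 is the only schedule of activities for patients with follicular lymphoma, and it serves both phases. Its row "Triplicate 12-Lead ECG" has marks at screening, Cycle 1 Days 1 and 5, Day 1 of the combined Cycles 3–6 column, end of induction, maintenance and end of maintenance. The Cycle 2 cells are empty. Footnote j narrows the induction marks: "ECGs will be performed in triplicate on Days 1 and 5 of Cycles 1 and 4 in the induction phase".

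The timing is tied to idasanutlin. Footnote j says "All ECGs should be performed within 2 hours prior to idasanutlin administration", and Section 4.5.7 gives the same window: "Pre-dose: within 2 hours prior to idasanutlin dosing". In both places the post-dose ECG is 6 hours after idasanutlin or after the antibody infusion, whichever is later.

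For Regimen B, Section 3.1.2.2 says "Obinutuzumab will be given alone in Cycle 1 and in combination with idasanutlin and venetoclax from Cycle 2 to 6". The Regimen B dosing grid in Appendix 1 agrees, with empty Cycle 1 cells for both oral drugs. The expansion grid in the same appendix allows Regimen B to be chosen there too.

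Appendix 3 has separate PK tables for Regimen B in both phases. They put the first post-dose idasanutlin and venetoclax samples on Cycle 2 Day 1 and the 2, 4 and 6 hour profile on Cycle 2 Day 5.

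Section 2.1 lists as a safety endpoint "Changes in vital signs, ECGs, and clinical laboratory results during and following study treatment administration".

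**The concern.** The PK schedule was adapted to Regimen B and the ECG schedule was not. Under Regimen B the first pair of induction ECGs is timed to a drug that is not given in that cycle, and the cycle in which both oral drugs start has no ECG.

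ECG change is a stated endpoint in both phases. In the bridging cohorts, doses for the next cohort are agreed once the last patient has finished the two-cycle observation period (Section 3.1.2.2), so that decision would be made without any scheduled ECG on idasanutlin or venetoclax. Section 4.5.7 also requires a repeat ECG when QTcF at a post-dose timepoint exceeds 500 ms or is 60 ms above baseline. For these two drugs, scheduled ECGs could first trigger that rule at Cycle 4.

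**Working it through.** The plan gives no figure to reproduce. The check is a comparison of tables plus day arithmetic.

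**Inputs.** Cycles last 28 days (Appendix 1). ECGs are on Days 1 and 5 of Cycles 1 and 4 (footnote j). Under Regimen B both oral drugs start on Cycle 2 Day 1; idasanutlin is given on Days 1–5 and venetoclax on Days 1–5 or 1–10 of a cycle. The dose-limiting toxicity window is the first two cycles (Section 3.1.2). No delays are assumed.

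**Timeline.** Day 1 of Cycle c is study day 28 × (c − 1) + 1.
- First oral doses, Cycle 2 Day 1: 28 × 1 + 1 = Day 29.
- End of the toxicity window: 28 × 2 = Day 56.
- First scheduled ECG on these drugs, Cycle 4 Day 1: 28 × 3 + 1 = Day 85.
- Gap: 85 − 29 = 56 days.
- Idasanutlin doses already taken (Cycles 2 and 3): 5 × 2 = 10.
- Venetoclax doses already taken: 5 × 2 = 10 or 10 × 2 = 20.

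Under Regimen A the same footnote gives ECGs on Days 1 and 5, around first exposure.

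If the grid mark in the Cycles 3–6 column were read as Cycle 3, the first ECG would be on Day 28 × 2 + 1 = Day 57. That is still 28 days after first exposure and one day past the window.

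**What each ECG day captures under Regimen B**

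| ECG day | Drugs given that day | Can the stated timing be met? | PK samples (Appendix 3) |
|---|---|---|---|
| Cycle 1 Day 1 | Obinutuzumab | Post-dose yes (end of infusion); pre-dose window refers to a drug not given | Obinutuzumab before and 30 min after infusion; idasanutlin and venetoclax pre-administration |
| Cycle 1 Day 5 | None | No; neither reference dose exists | None |
| Cycle 2 Days 1 and 5 | Both oral drugs; obinutuzumab on Day 1 | No ECG scheduled | Oral drugs pre-dose and 6 h; also 2 and 4 h on Day 5 |
| Cycle 4 Days 1 and 5 | Both oral drugs; obinutuzumab on Day 1 | Yes | Oral drugs pre-dose and 6 h |

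No Regimen B exception for ECGs appears in Section 4.5.7, elsewhere in the protocol, or in the SAP.

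**The case against.** The case for a small effect is a fair one, and much of it stands.

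- **Cycle 4 can stand in for first exposure.** The protocol gives a half-life of about 1 day for idasanutlin and about 17 hours for venetoclax, the latter without accumulation in CLL/SLL. The drug-free interval is 23 days after a 5-day idasanutlin block and 18 days after a 10-day venetoclax block: 23 half-lives, and 18 × 24 / 17 ≈ 25 half-lives. A pre-dose ECG at Cycle 4 is therefore close to drug-free, and the 6-hour ECG resembles a first dose. What is lost is early timing, and the patients who stop before Cycle 4.
- **Exposure–ECG pairs exist.** A reader might infer that PK and ECG no longer match at all, or that the Cycle 1 ECGs have no concentrations. Appendix 3 does not support either reading: Cycle 4 has pre-dose and 6-hour samples at the ECG times, and Cycle 1 Day 1 has the samples shown above.
- **No dilution of a planned analysis.** A reader might also infer that off-drug Cycle 1 readings would weaken an estimated ECG effect. The SAP's ECG table (Output 57) shows shifts from baseline only at end of induction and end of maintenance. It pools no on-treatment readings, but it does not fill the Cycle 2 gap either.
- **Prior QTcF data are reassuring.** The protocol reports no apparent QTcF relationship for idasanutlin, or for venetoclax up to 1200 mg, which is above this study's 800 mg cap. These passages report no data on the triplet. Appendix 13 lists one QT-prolongation event among 34 patients on 5-day idasanutlin, with another formulation and no grade.
- **Unscheduled ECGs are allowed** when clinically indicated (Section 4.5.7).

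These points limit the consequence. They do not give Cycle 1 Day 5 a dose to be timed against, or put a scheduled ECG in the cycle where both oral drugs start.

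**Conclusion.** The inconsistency holds. For Regimen B, footnote j, the ECG row and Section 4.5.7 conflict with the dosing and PK tables. One of the four induction ECG days (Cycle 1 Day 5) has no study drug to refer to, and another (Cycle 1 Day 1) can be timed only to obinutuzumab. The first scheduled ECG on idasanutlin and venetoclax is on Day 85, 56 days after first exposure and 29 days after the toxicity window closes (85 − 56). Patients who stop before Cycle 4 have no scheduled induction ECG on these drugs.

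This rests on undelayed 28-day cycles and concerns scheduled ECGs only. It affects the Regimen B bridging cohorts and, if Regimen B is selected, the approximately 40 expansion patients with follicular lymphoma. The documents do not show that a QT signal would be missed altogether or that a planned estimate would be biased. The weakness is in early safety information and in whether the schedule can be carried out as written. It should be corrected, at little cost.

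**What to change.** Reconcile the passages by adding a Regimen B version of footnote j and of the ECG row in Appendix 1, with a matching line in Section 4.5.7:

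- The idasanutlin-timed ECGs follow the first idasanutlin/venetoclax cycle, on Days 1 and 5 of Cycle 2, as Appendix 3 already does for PK. Cycle 4 is unchanged.
- The Cycle 1 Day 5 ECG, which has no reference dose, is dropped.
- The text states whether the Cycle 1 Day 1 ECG is kept around the first obinutuzumab infusion. If so, its timing is given relative to the infusion.

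The last item needs an explicit decision. Simply moving both Cycle 1 ECGs would leave none around the first infusion. The protocol says infusion reactions occur mainly in Cycle 1, most often on the first day (Section 1.2.2.2), and that cardiac events may occur as part of them (Section 5.1.1.7).

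The cost is amendment wording. Induction ECG days go from four to five per Regimen B patient if Cycle 1 Day 1 is kept, and stay at four if it is not. Patients already attend Cycle 2 Days 1 and 5 for sampling up to 6 hours post-dose, so no visit is added. Dosing is not affected.

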#### **5.1.6 Prophylaxis and Monitoring for Tumor Lysis Syndrome**

TLS is a risk for patients with NHL who are treated with high cell-killing agents, including venetoclax. Changes in blood chemistries consistent with TLS that require prompt management can occur as early as 6 to 8 hours following the first dose of venetoclax. The risk of TLS is a continuum based on multiple factors, including tumor burden and comorbidities. Risk is highest for patients with bulky disease, elevated leukocyte count, elevated pretreatment LDH levels, compromised renal function, and dehydration. Assessment of tumor burden with CT scan and CBC with WBC differential, as well as blood chemistry (potassium, uric acid, phosphorus, calcium, and creatinine), should be performed in all patients and correct preexisting chemistry abnormalities prior to initiation of treatment with venetoclax.

All patients must receive prophylaxis for TLS before the initiation of the first dose of venetoclax (see also Section 4.3.2.5). Prophylaxis will include the following:

- Appropriate hydration, consisting of a fluid intake of approximately 2–3 L/day starting 24–48 hours before the start of treatment
- Administration of an agent to reduce uric acid (such as allopurinol 300 mg/day orally beginning 72 hours before dose and continuing for 3–7 days afterwards) or

rasburicase IV (for those high risk patients with elevated uric acid levels before treatment, or when otherwise judged to be appropriate by the investigator) until normalization of serum uric acid and other laboratory evidence of TLS (e.g., elevated serum LDH levels)

- Laboratory results should be reviewed and electrolyte values should not demonstrate any clinically significant abnormalities before the first dose of venetoclax, or the patient should receive additional prophylactic treatment and hydration before the initiation of dosing
- Patient at higher risk of TLS will be hospitalized for the initial venetoclax dose. Patients not considered at higher risk of TLS may be hospitalized after discussion with the investigator and Medical Monitor

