On the day of the initial visit with administration of venetoclax (Day 1 of Cycle 1), serial vital signs, serum chemistry, and hematology samples will be drawn before the dose of venetoclax and 8 and 24 hours following the dose (see [Appendix 1](#) and [Appendix 2](#)). These samples are to be sent immediately to the laboratory and the investigator or designee must review the results promptly. Laboratory values obtained prior to venetoclax dosing are to be used to determine whether a patient developed a change related to TLS. Laboratory results obtained 24 hours post-dose must be reviewed before receiving the dose of venetoclax on that day. Patients who develop electrolyte changes suggestive of TLS should undergo aggressive management and further monitoring according to the guidance in [Appendix 12](#), Recommendations for Initial Management of Electrolyte Imbalances and Prevention of Tumor Lysis Syndrome.

In addition, if TLS is observed in the initial cohorts, staggering the dosing of venetoclax may be explored (venetoclax dosing may be initiated 2 or 3 days after the first idasanutlin dose during the first cycle of therapy), or starting at a lower dose of venetoclax and reaching the specified dose in a step-wise fashion after discussion with the Medical Monitor to prevent or promptly treat TLS.

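### In Regimen B, footnote q and Section 5.1.6 date the tumor lysis laboratory draws to Cycle 1 Day 1, although venetoclax starts on Cycle 2 Day 1; the instruction is inconsistent, not absent

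*Protocol*

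**What the plan says.** Protocol Section 3.1.2.2 and the Regimen B treatment table in Appendix 1 start idasanutlin and venetoclax in Cycle 2. The expansion-phase table in Appendix 1 (footnote c) allows the same schedule there if Regimen B is selected. Appendix 1 is the only schedule of activities for follicular lymphoma and serves both regimens.

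Five instructions bear on the TLS samples:

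- **Footnote q**, attached only to the Cycle 1 Day 1 hematology and chemistry cells: "Additional hematology and serum chemistry samples must be drawn 0–4 hours pre-dose and 8 and 24 hours post-dose on Day 1 of Cycle 1". It puts the 24 h sample on Cycle 1 Day 2.
- **Footnote r**, the only footnote on the Cycle 2 Day 1 laboratory cells: "Perform hematology and serum chemistry tests within 72 hours prior to Day 1 of each cycle".
- **Footnote g**, on the vital-signs row, which is ticked at Cycle 2 Day 1: TLS chemistry "prior to the first dose of venetoclax and 8, 12, and 24 hour post-dose", with no cycle number.
- **Section 5.1.6**: "On the day of the initial visit with administration of venetoclax (Day 1 of Cycle 1"; the parenthesis closes there. Serial vital signs are to be taken, and "serum chemistry, and hematology samples will be drawn before the dose of venetoclax and 8 and 24 hours following the dose".
- **Section 5.1.7.2**, for hospitalized patients: chemistry before the first venetoclax dose and 8, 12 and 24 h after it, and hematology at 8 and 24 h.

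Section 5.3.5.11 also describes the planned TLS hospitalization as a Cycle 1 Day 1 event.

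**The concern.** The draws exist to catch TLS at the first exposure to venetoclax. Section 5.1.6 says that the relevant chemistry changes "can occur as early as 6 to 8 hours following the first dose of venetoclax". It sets the reference for judging them: "Laboratory values obtained prior to venetoclax dosing are to be used to determine whether a patient developed a change related to TLS". It also sets a gate on further dosing: "Laboratory results obtained 24 hours post-dose must be reviewed before receiving the dose of venetoclax on that day". In Regimen B, footnote q and the parenthesis in Section 5.1.6 date all of this one cycle before any venetoclax is given.

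Sites commonly build visit worksheets from the schedule of activities. Read along the laboratory rows, Cycle 2 Day 1 shows a pre-cycle sample and nothing after the dose. The general note to Appendix 1 points the same way, since assessments on treatment days are done before dosing unless stated otherwise. At stake is whether the post-dose samples, including the one that gates the next venetoclax dose, are reliably taken.

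**Working it through.** This is a comparison of text; there is no planned statistic to reproduce.

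**Timing.** Cycles last 28 days, so the first venetoclax dose in Regimen B falls on nominal study day 28 + 1 = 29. Footnote q places its draws on study days 1 and 2.

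**The instructions side by side, for a Regimen B patient:**

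| Source | Anchored to | Pre-dose sample | Post-dose chemistry | Post-dose hematology |
|---|---|---|---|---|
| Footnote q | Cycle 1 Day 1 (obinutuzumab only) | 0–4 h | 8, 24 h | 8, 24 h |
| Footnote r at Cycle 2 Day 1 | Start of cycle | Within 72 h | None | None |
| Footnote g | First venetoclax dose | Before the dose, no window (chemistry) | 8, 12, 24 h | None |
| Section 5.1.6 | First venetoclax visit, labelled Cycle 1 Day 1 | Before the dose, no window | 8, 24 h | 8, 24 h |
| Section 5.1.7.2 (hospitalized only) | First venetoclax dose | On admission and before the dose | 8, 12, 24 h | 8, 24 h |

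**Post-dose timepoints required at Cycle 2 Day 1:**

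- Laboratory cells alone (footnote r): 0.
- Footnote g: 3 for chemistry, 0 for hematology.
- Section 5.1.6 read without its parenthesis: 2 for each.

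**What this leaves:**

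1. Post-dose chemistry is required for every patient through footnote g.
2. Post-dose hematology is securely required only for hospitalized patients. For the others it rests on the mislabelled sentence in Section 5.1.6.
3. The 0–4 h pre-dose window is stated only in footnote q. Footnote g and Section 5.1.6 say only that the sample precedes the dose.

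**Was the difference intended?** Other parts were fitted to Regimen B. Table 7 ties TLS prophylaxis to the first cycle that contains venetoclax, and the Regimen B pharmacokinetic schedule in Appendix 3 puts its first post-venetoclax sample, at 6 h, on Cycle 2 Day 1. Footnote q and the parentheses in Sections 5.1.6 and 5.3.5.11 look like places that this update did not reach.

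**Patients under the wording.** One bridging cohort has 3 to 6 patients (Section 3.1.2). If Regimen B is also chosen for the 40 expansion patients with follicular lymphoma (Section 3.1.3), the range is 40 + 3 = 43 to 40 + 6 = 46, and more if further bridging cohorts open.

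**The case against.** The strongest reply is that the monitoring that matters is already required at the right dose. Footnote g is in the same schedule, on a row ticked at Cycle 2 Day 1, and supplies both an 8 h sample and the 24 h sample that gates the next dose. Section 5.1.6 is triggered by the venetoclax visit; its parenthesis cannot be followed literally in Regimen B, because no venetoclax is given that day. Section 5.1.7.2 covers mandatory high-risk admissions and any other hospitalized patient. Appendix 12 acts on laboratory results in the 24 h after the first dose. A site would have to overlook several instructions before chemistry was missed.

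That stands, and it rules out several stronger readings:

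- **That Regimen B has no TLS monitoring at the first venetoclax dose.** Footnote g says otherwise.
- **That the chemistry reference could be up to 72 h old.** Footnote r's sample is a separate routine draw that also applies at Cycle 1 Day 1, and footnote g asks for its own sample before venetoclax. Setting 4 h against 72 h does not describe the TLS chemistry baseline.
- **That the Cycle 1 Day 1 draws are misplaced.** Footnote q names no drug, and Section 5.1.1.2 reports TLS, some of it fatal, with obinutuzumab. The draws belong there; they are simply not repeated at Cycle 2.
- **That TLS counts or an endpoint would be affected.** The laboratory TLS definition in Appendix 5 uses no hematology value, and nothing in the documents shows samples being missed.

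The reply does not make the text consistent. Footnote g sits on the vital-signs row and is silent on hematology. Section 5.1.6 sends the reader back to Appendix 1, where the laboratory rows point to Cycle 1.

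**Conclusion.** Wrong as written, with a narrow consequence. An operational safety instruction names the wrong day for Regimen B in footnote q's laboratory rows and in Section 5.1.6, while footnote g names the right dose. The gap that remains is post-dose hematology for non-hospitalized patients and the 0–4 h pre-dose window. Beyond that there is a risk, conditional on a site following footnotes q and r and overlooking the dose-anchored text, that the post-dose draws are missed.

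The wording would apply to 3–6 patients in one bridging cohort. The 43–46 figure assumes that Regimen B is selected and the expansion enrolls all 40. These are patients under the wording, not a forecast of missed samples. The documents give no hospitalized share, so the number whose hematology rests on Section 5.1.6 alone cannot be stated. The reading of the text is secure; the practical harm is possible but not shown. It should be corrected at the next amendment.

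**What to change.** Keep the Cycle 1 Day 1 draws, then:

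1. Add to footnote q of Appendix 1: *and on Day 1 of the first cycle including venetoclax (Cycle 2 Day 1 in Regimen B), with the 24 h sample on Day 2 of that cycle*.
2. Attach footnote q to the Cycle 2 Day 1 hematology and chemistry cells for Regimen B.
3. In Section 5.1.6, replace the Cycle 1 Day 1 parenthesis with *Day 1 of the first cycle including venetoclax*.
4. Make the same replacement in Section 5.3.5.11, so that a planned TLS admission in Cycle 2 clearly falls under the exemption from adverse event reporting.
5. Leave footnote g unchanged, including its 12 h chemistry sample.

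The cost is one footnote, two cells and two parentheses, in wording that Table 7 already uses. No new type of procedure is added, since footnote g and Section 5.1.6 already call for samples around the first venetoclax dose.
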